#### 6.4 Missing data

The occurrence of missing data in this trial is expected to be low and, when present, is expected to be equally distributed across the 2 treatment groups. We estimate that careful selection of patients during the screening phase and the consent process should result in no more than 10% missing data from patients who drop out before completing the full 15 week treatment period and the 3 week post-treatment follow-up. In the primary, intention-to-treat analysis, patients with a pattern of missing data that precludes determination of the primary outcome according to its definition will be counted as unimproved.

The proportions with missing data will be compared across treatment groups using  $\chi^2$  tests. If the amount of missing data exceeds 10%, then a variety of sensitivity analyses will be carried out to compare to the primary analysis using all available non-missing data and assuming that the missingness is either missing completely at random (MCAR) or missing at random (MAR): (1) compare pessimistic and optimistic imputations of the missing values, (2) correct for missing data using multiple imputation with 10 replicated samples, and (3) use mixed random effects logistic or linear regression models, depending on the type of outcome measure. It is possible that the missingness is not MCAR or MAR, but is missing not at random (MNAR). Few statistical methods are available when there are non-ignorable missing data patterns and these may be employed to assess sensitivity of the results to non-ignorable missing data if the level of missing data exceeds 10%; however, all such methods involve strong assumptions that cannot be verified from the available data.

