**Sample size justification**

- Total of 130 patients in 2 groups of equal size (65 per group)
- Primary comparison: nortriptyline vs. placebo
- Error protection: Type I = 0.05 and Type II = 0.10 (90% power)
- Minimum clinically important difference (MCID): 50% reduction in GCSI outcome (see below) during 15 weeks of treatment
  - Expected percent with improved GCSI in the placebo group: 30%
  - Expected percent with improved GCSI in the nortriptyline group: 60%
  - Source of estimates of MCID: Consensus of GpCRC clinicians
- Statistical test and sample size software
  - Chi-squared test for two proportions
  - Dupont and Plummer PS software

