### 6.3 Statistical analysis

The primary analysis will be made on “intention to treat” basis, which means that all randomized patients with GCSI scores at baseline and at any time during 15 weeks of treatment will be analyzed in the treatment group to which they were assigned. Any randomized patient who does not have the requisite GCSI scores will be treated as a non-responder and compared by assigned treatment group. Primary comparisons will be of the full nortriptyline group versus the full placebo group. Secondary, sensitivity analyses on a per-protocol basis will also be carried out, excluding patients from both groups who do not complete at least 60% (9 weeks) of the 15 weeks on assigned treatment.

Since the primary outcome measure is a binary indicator of improvement in GCSI score and since the randomization is stratified by clinic, P-values will be derived from the Mantel-Haenszel  $\chi^2$  test for stratified 2x2 tables, with stratification by clinic, comparing proportions improved in the group assigned to nortriptyline compared to the group assigned to placebo. The P-values so derived will be reported in the primary paper on the results of the trial. A P-value of 0.05 will be considered statistically significant.

Given the randomized design and adequate size planned for the NORIG trial, it is unlikely that confounding of the treatment groups by covariates related to the change in GCSI score will occur. However, if confounding should occur, sensitivity analyses using logistic regression models with GCSI score improvement as the binary response and treatment group indicator and any suspected confounders as covariates will be carried out to determine the sensitivity of the primary P-value to confounding; however, the Mantel-Haenszel derived P-value will be the primary P-value reported.

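### Ten imputations are few for a sensitivity analysis that starts only above 10% missing data: its pooled P-value is noisy when close to 0.05

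*Protocol*

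**What the plan says.** Protocol section 6.4 expects that careful selection "should result in no more than 10% missing data from patients who drop out". If that expectation fails, further analyses follow: "If the amount of missing data exceeds 10%, then a variety of sensitivity analyses will be carried out". There are three: pessimistic and optimistic imputations, multiple imputation, and mixed random-effects models. For the second, the number of imputations is fixed: "correct for missing data using multiple imputation with 10 replicated samples". The number does not rise with the amount missing, and no Monte Carlo error criterion goes with it.

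The primary analysis does not use multiple imputation. Under 6.4, "patients with a pattern of missing data that precludes determination of the primary outcome according to its definition will be counted as unimproved". Section 6.3 says that "the Mantel-Haenszel derived P-value will be the primary P-value reported", stratified by clinic, and sets the threshold for that analysis: "A P-value of 0.05 will be considered statistically significant".

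**The concern.** A small number of imputations is usually justified by the efficiency of the point estimate, and on that ground ten is enough. A P-value is less forgiving. The pooled estimate and the between-imputation variance both carry simulation error, and near 0.05 a small shift in the test statistic moves P visibly. Section 6.4 uses this analysis for comparison with a primary result that is itself judged at 0.05, and only when missingness is above what was planned for. At stake is how stable a robustness check is when its answer is close. The primary result is not at stake.

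**Working it through.** **The plan's own figure.** Section 6.5 gives 56 per group for 0.30 versus 0.60, two-sided alpha 0.05, 90% power. With the section's formula:

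n = [1.960·√(2·0.45·0.55) + 1.282·√(0.30·0.70 + 0.60·0.40)]² / 0.30² = (1.379 + 0.860)² / 0.09 = 55.7, so 56.

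This agrees. At the planned 65 per group, power is 93.9%.

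**Efficiency of ten imputations.** Relative efficiency is 1/(1 + γ/m), where γ is the fraction of missing information. With m = 10 it is 0.990 at γ = 0.10, 0.980 at 0.20 and 0.971 at 0.30. The estimate loses almost nothing.

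**Seed dependence of the P-value.**

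- From the protocol: 65 per arm, m = 10, threshold 0.05, placebo response about 0.30.
- Assumed: equal missingness in both arms, at shares of about 11%, 20% and 30%; a missing binary outcome imputed within arm from a Beta posterior with prior (0.5, 0.5).
- One borderline data set per share, with nortriptyline responders chosen so that the completers' P is as near 0.05 as whole numbers allow. At 11%, 27/58 versus 17/58 gives a difference of 0.172, standard error 0.0887, z = 1.94 and P = 0.052.
- Pooling by Rubin's rules: T = U + (1 + 1/m)·B, λ = (1 + 1/m)·B/T, df = (m − 1)/λ², where U is the mean within-imputation variance and B the between-imputation variance of the risk difference.
- The data were held fixed and only the random draws changed, over 40,000 repeats.

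| Missing | Observed per arm | Responders | m | 95% range of P | SD of P | Seeds with P<0.05 |
|---|---|---|---|---|---|---|
| 11% | 58 | 27 v 17 | 10 | 0.030-0.090 | 0.015 | 41% |
| 11% | 58 | 27 v 17 | 100 | 0.044-0.062 | 0.0045 | 32% |
| 20% | 52 | 26 v 16 | 10 | 0.018-0.096 | 0.020 | 61% |
| 20% | 52 | 26 v 16 | 100 | 0.032-0.054 | 0.0056 | 91% |
| 30% | 46 | 23 v 14 | 10 | 0.018-0.138 | 0.031 | 42% |
| 30% | 46 | 23 v 14 | 100 | 0.037-0.070 | 0.0084 | 43% |

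A second simulation imputed the visit scores under monotone dropout and then derived the two-consecutive-visit response. In data sets with a converged P of 0.04-0.06, m = 10 gave 0.033-0.073 at 12% dropout, 0.031-0.082 at 20% and 0.027-0.093 at 30%. With m = 100 the ranges were 0.043-0.055, 0.043-0.058 and 0.041-0.061. The direction is the same and the spread somewhat narrower, so the exact ranges depend on the model.

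**Away from the border.** At the design rates of 0.60 versus 0.30, with m = 10 and 11-30% missing, at least 99.9% of seeds give P<0.05.

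**How often the border is reached.** For an unstratified chi-squared test with 46 to 65 analysed per arm, the probability that P falls in 0.04-0.06 is about 2-4% at 0.60 versus 0.30, and about 5-7% at an assumed weaker effect of 0.56 versus 0.33.

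**How far more imputations help.** The SD falls with 1/√m. To bring it to 0.005 from the m = 100 values takes about 100·(0.0056/0.005)² = 125 imputations at 20% missing and 100·(0.0084/0.005)² = 282 at 30%. At 11% missing, 100 is already enough. Even then, suppose the converged P is spread evenly over 0.04-0.06 with roughly normal seed noise of 0.005. The average of Φ(−|P − 0.05|/0.005) over that interval is about 0.20, so one seed in five would still land on the other side of 0.05.

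**The case against.** The strongest reply is that no conclusion rests on this P-value. It comes from one of three sensitivity analyses, and section 6.4 attaches no rule to its falling above or below 0.05. The mixed models address the same question without imputation draws. Ten imputations are not an error either: Rubin's rules carry a finite-m term, so the inference is valid. Seed and imputation model may be set in the statistical analysis plan, and the protocol's silence on them is no fault. A recorded seed would by itself make a run repeatable.

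Most of this stands, and it limits the point. A reader might infer that the seed could decide the trial, or that two analysts following the plan would reach opposite trial conclusions. The protocol does not support that, because its reported P-value is the Mantel-Haenszel one, with undeterminable outcomes counted as unimproved. The shares of seeds below 0.05 in the table should also not be read as risks for this trial, because they are conditional on borderline data chosen for the purpose.

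What remains is that the protocol states a specific number, and this number leaves avoidable noise in a result meant for comparison with the primary one. A recorded seed makes one run repeatable but does not bring its P-value closer to the converged value.

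**Conclusion.** The point holds as a minor improvement. With ten imputations, a pooled P near 0.05 has a seed-driven standard deviation of about 0.015 at 11% missing, 0.020 at 20% and 0.031 at 30%. These figures rest on assumed missing shares, equal missingness by arm and a simple imputation model; a visit-level model gives narrower ranges. The effect matters only if missingness exceeds 10% and the imputed result is close to 0.05, the latter in about 2-7% of trials at response rates near those planned. Validity, the efficiency of the estimate and the primary analysis are untouched.

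**What to change.** In section 6.4, replace the ten replicated samples with at least 100 imputations, increased until the Monte Carlo standard error of the P-value is small, for example below 0.005. Report that error next to the pooled estimate and P-value. Recording the seed in advance is sensible and can be left to the statistical analysis plan. A converged P almost exactly at 0.05 will still vary by seed; the reported Monte Carlo error lets the reader see this. The cost is a small change of wording in 6.4 and a little computing time, with no change to patients, visits or the primary test.

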### 6.5 Justification of sample size

The planned sample size for the NORIG trial is 130 patients with equal allocation to each of the two treatment groups (65 per group).

We based the sample size estimates on a two-group, binomial comparison of the proportions of patients satisfying the primary outcome, improvement in the GCSI score over the course of treatment. For sample size purposes, the expected proportions improved (0.6 in the nortriptyline group compared to 0.3 in the placebo group), were derived from the expert opinions of clinicians on the GpCRC Steering Committee, based on their experience with the GCSI in patients with idiopathic gastroparesis similar to those meeting the eligibility criteria for the trial. The size of the smallest clinically meaningful effect (0.60 vs 0.30 response rates) was also based on the expert opinion of Steering Committee, taking into account the expected missing data rate of 10% and its consequent reduction in improvement rates.

The sample calculations were performed using the nQuery Advisor 5.0^33 software, which uses the formula:

$$n = \frac{\left[ z_{1-\alpha/2} \sqrt{2\bar{\pi}(1-\bar{\pi})} + z_{1-\beta} \sqrt{\pi_1(1-\pi_1) + \pi_2(1-\pi_2)} \right]^2}{(\pi_1 - \pi_2)^2}$$

where,

$n$  = sample size per group

$\pi_1$  = expected proportion with 50% improved GCSI in placebo group (assumed=0.30)

$\pi_2$  = expected proportion with 50% improved GCSI in nortriptyline group (0.60)

$\bar{\pi}$  = average of  $\pi_1$  and  $\pi_2$

$\alpha$  = Two-sided type I error (0.05)

$\beta$  = Type II error (0.10; i.e., 90% power)

The number per group, using the above formula is 56 for a total of 112. To allow for possible mis-specification in the estimated response rates used in the calculation, we propose a sample size of 65 patients per group, or a total of 130 for the trial.

### 6.6 Interim analysis

An independent Data and Safety Monitoring Board (DSMB), appointed by the NIDDK, is responsible for approving the protocol for the NORIG trial and for monitoring the accumulated interim data as the trial progresses to ensure patient safety and to review efficacy. The DSMB is a multi-disciplinary group with a written charge provided by the NIDDK. The DSMB reports to the NIDDK, which will, in turn, communicate DSMB recommendations to the investigators, as appropriate.

The DSMB meets to approve the protocol. After the trial commences, the DSMB meets twice a year to review data or other issues. The DSMB may request more frequent meetings if necessary to fulfill its charge. It may also request additional safety reports on a more frequent basis.

Interim data on safety measures requested by the DSMB are reviewed at each of the scheduled semi-annual full meetings. Two additional written safety reports will be reviewed by the DSMB between scheduled full meetings. Serious adverse events will be reviewed by the DSMB as they occur with the option of a teleconference discussion if any DSMB member so requests.

The DSMB reviews one planned interim analysis of the primary outcome measure. O'Brien-Fleming statistical stopping guidelines for efficacy apply. This interim efficacy analysis will occur when approximately 50% of the data are complete or when approximately 65 of the 130 patients have completed the 18 week trial. The interim monitoring bounds were adjusted for one interim look as follows: We propose guidelines (boundaries) with O'Brien-Fleming Type 1 error spending functions for the primary outcome.

The DSMB also reviews the overall progress of the trial in terms of recruitment and data quality and makes a formal recommendation to the NIDDK at the end of each scheduled meeting as to whether the trial should continue unmodified, continue with protocol modifications, or be stopped.

---

## NORIG Trial Protocol

### 7. Human subjects issues

---

#### **Overview and IRB approval**

The study protocol and consent form will be submitted to each clinical center's IRB. Additionally, each clinical center will submit to their IRB any recruitment materials to be used at their site. A clinical center may not initiate any patient contact about the NORIG Trial until the center has IRB approval and the DCC has certified the center for initiation of patient activities. Consent forms must have IRB approval. Centers must provide the DCC with copies of the initial IRB approval notice and subsequent renewals, as well as copies of the IRB approved consent statement. All study personnel will have completed training in the Protection of Human Subjects per NIH guidelines.

The proposed study anticipates recruiting a significant proportion of women and racial/ethnic minorities (African American, Hispanics or Latino, Asian, American Indian/Alaska Native, Native Hawaiian or other Pacific Islander) as well as non-Hispanic white subjects. We anticipate that the patients will be recruited from diverse sources, largely from tertiary referral populations and will represent the entire spectrum of idiopathic gastroparesis.

All subjects enrolled in the NORIG Trial will receive the standard of care for idiopathic gastroparesis and identified associated medical problems as defined by the GpCRC Steering Committee (see Standards of Care for Patients with Gastroparesis). This will include provision of health care counseling and educational materials at enrollment and during follow-up.

#### **Informed Consents**

A prototype consent will be prepared for the study. Individual centers may add material but may not delete material thought to be necessary for informed consent. Centers may reformat and reword information to conform to their local IRB requirements. A signed consent form will be obtained from the subject. The consent form will describe the purpose of the study, the procedures to be followed, and the risks and benefits of participation. A copy of the consent form will be given to the subject and this fact will be documented in the subject's record.

#### **Confidentiality**

All laboratory specimens, evaluation forms, reports, and other records that are part of the study data collection and entry materials will be identified by coded number only to maintain subject confidentiality. All records will be kept in locked file cabinets with access limited to GpCRC investigators. All computer entry and networking programs will identify patients by patient identification number. Clinical information will not be released without written permission of the subject, except as necessary for monitoring by the IRB or DSMB. Clinical information may be reviewed during site visits, but use of personal identifiers will be avoided. Consent procedures and forms, and the communication, transmission and storage of patient data will comply with individual center IRB and NIH requirements for compliance with The Health Insurance Portability and Accountability Act (HIPAA).

---

## 9.2 Data collection schedule

Assessment/Procedure	Screening Visits			Follow-up visits Weeks from randomization					
	s1	s2	rz	3	6	9	12	15	18
Consent	X	.	.	.	.	.	.	.	.
Gastric emptying scintigraphy review	X	.	.	.	.	.	.	.	.
Upper endoscopy review	X	.	.	.	.	.	.	.	.
Baseline medical history	X	.	.	.	.	.	.	.	.
PAGI-SYM questionnaire	X	.	.	X	X	X	X	X	X
GSRS questionnaire	X	.	.	X	X	X	X	X	X
SF-36 QOL questionnaire	X	.	.	.	.	X	.	X	.
Beck Depression Inventory-II	X	.	.	X	X	X	X	X	X
State Trait Anxiety Inventory	X	.	.	.	.	X	.	X	.
Brief Pain Inventory	X	.	.	.	.	X	.	X	.
PHQ-15 questionnaire	X	.	.	.	.	X	.	X	.
Electrocardiogram (ECG)	X	.	.	.	.	X	X	.	.
Physical exam	X	.	X	.	.	X	X	X	.
Satiety test with electrogastrography (EGG)	.	X	.	.	.	.	X	.	.
Study drug dispensed	.	.	X	X	X	X	X	.	.
Review of study drug adherence	.	.	.	X	X	X	X	X	X
Follow-up medical history including review of adverse events	.	.	.	X	X	X	X	X	X
Labs	.	.	.	.	.	.	.	.	.
CBC, metabolic and hepatic panel	X	.	.	.	.	.	X	.	.
TSH	X	.	.	.	.	.	.	.	.
Plasma banking	.	X	.	.	.	.	X	X	.
DNA banking	.	X	.	.	.	.	.	.	.
Pregnancy test	X	.	X	.	.	X	X	X	.

**Physical exam:** includes measurement of weight, height, waist and hip circumferences, vital signs (temperature, heart rate, blood pressure) general physical findings

**CBC:** Complete blood count: white blood cell count, red blood cell count, hemoglobin, hematocrit, platelet count

**Metabolic panel:** sodium, potassium, chloride, carbon dioxide, glucose, calcium, magnesium, blood urea nitrogen (BUN), creatinine.

**Hepatic Panel:** albumin, total protein, bilirubin, alkaline phosphatase, alkaline aminotransferase (ALT), aspartate aminotransferase (AST)

**TSH:** Thyroid Stimulating Hormone

